Assessment Schedule: The clinical assessments will be administered prior to administration of the study medication, immediately prior to the MRI scan, upon completion of the MRI scan, and at the follow-up safety assessment, which will be conducted 75 min after the completion of the MRI scanning. The cognitive assessments will be conducted prior to the administration of the study medication and after the MRI scanning is completed and the participant has had lunch. The laboratory assessments will be collected at pre-TRYP challenge baseline, and 30 min, 60 min and 90 min post ingestion. The final laboratory assessment will be collected at the time of the second administration of the cognitive battery. The safety assessments will be administered

prior to administration of the study medication, every 30 min after medication administration, upon completion of the MRI scan, and at the follow-up safety assessment.

Table 1. Assessment Schedule.

	Study Lead In (up to 2 weeks)	Challenge Visit: Estimated Time of Assessment	Challenge Visit: Actual Time of Assessment	Initials
Informed Consent, ESC	X			
SCID and diagnostic interview, MRI screening	X			
Medical Screening Medical Hx, physical exam, blood draw, urinalysis, toxicology screen, pregnancy test (females), EKG, medication use screening, caffeine use screening, Birth Control Selection (females)	X			
Clinical Stability Determination (schizophrenia group only seen on two visits, healthy controls one visit) 2 unchanged CGIs	X			
Mock scanning session	X			
Scheduling of 2 challenge visits and NPO order for 12 hours in advance of admission on challenge study days	X			
Participant Admission/BSU Arrival Review of Study Procedures and retrospective recall of food intake (past 12 hours). Collect personal items not safe during MRI testing.		7:30 am		
Urine pregnancy (females), expired CO, urine toxicology and blood alcohol testing, MRI screening		7:45 am		
Insertion of indwelling IV line, fluids, period of relaxation		8:00 am		
Laboratory Assessments (1): cortisol, ACTH, kynurenine, KYNA, 3-HK, cytokines		8:15 am		
Cognitive Measures (1): HVLT-R, BACS Symbol Coding, BVMT, CPT-IP, WMS®-		8:30 am		

III, LNS				
Vital signs, SEC, SSS Clinical Assessments (1): BPRS, SANS, CDS, CGI		9:15 am		
Oral Administration of Medication (Tryptophan 6 gram/ Placebo)		10:00 am		
Protein Free Snack		10:15		
Vital signs, SEC, SSS Laboratory Assessments (2)		10:30		
Vital signs, SEC, SSS Laboratory Assessments (3)		11:00 am		

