Statistical Analysis: Initially, we will examine responses to TRYP or placebo challenge separately in healthy controls and participants with schizophrenia-related disorders (SRD), anticipating that different basal states of KYNA metabolism may result in distinct responses to TRYP challenge in the two groups. Secondary analyses will compare responses to TRYP challenge in the two groups.

Primary Aims:

- 1): To determine if TRYP-induced elevated KYNA levels impair performance on neuropsychological measures of attention, processing speed verbal and visual memory, and working memory.

Analysis plan: To facilitate comparison of the magnitude of effects across the six cognitive tests from the MCCB, we will utilize the MCCB T-scores for each test. For each cognitive measure, we will fit a mixed model for repeated measures ANCOVA: post-study drug score on i-th day = pre-study drug score on i-th day + treatment on i-th day + day + treatment x day, where day (=1,2) is an indicator of whether the scores were collected on the first or second day of testing. In this model, the treatment effect estimates the average TRYP - placebo difference across the two possible orders of testing, and the treatment x day effect estimates how much this difference might depend on whether TRYP or placebo was administered first. Learning effects from repeated cognitive testing could produce diminishing increases across the four repeated administrations of each test, resulting in larger pre-post differences in scores on the first versus second day of testing; these learning effects could be different following dosing with TRYP versus placebo, masking the existence of treatment x day interactions. Since the MCCB tests were chosen to have small learning effects ($d < 0.1$; 101), we anticipate these learning effects and possible interactions with treatment will be small. To take account of multiple testing with six cognitive tests, we will use the Benjamini-Hochberg False Discovery Rate (FDR; 120) modification of the Bonferroni method: we will compare the six p-values from largest to smallest to successively stricter critical values $c_j = 0.05 \times (6-j+1)/6$; if the j-th p-value is less than c_j , we will reject that null hypothesis and all null hypotheses corresponding to smaller p-values. To compare the magnitude of T-score differences between TRYP and placebo among cognitive tests, we will add terms for cognitive test and test x treatment interactions to the model described above.

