Analysis Plan: For exploratory analysis of changes in neural activation and functional connectivity in the default mode network (i.e., medial temporal lobe, mPFC, posterior cingulate cortex, ventral precuneus and medial, lateral and inferior parietal cortex) in healthy controls and participants with SRDs given TRYP or placebo, we will use models similar to those outlined for Specific Aim 2.

2): To examine if baseline and/or post-challenge HPA axis and inflammatory indices moderate or mediate the response of behavioral or functional measures to TRYP-induced elevated KYNA levels.

Analysis Plan: We will conduct exploratory analyses at unadjusted two-sided alpha = 0.05. People with SRD have been reported to have higher brain KYNA levels than healthy controls, and have major differences in behavioral and functional measures. Accordingly, we will analyze mediating and moderating effects of KYNA separately in the two groups, following the approach of Kraemer et al (118). To test moderation, we will examine the repeated measures models: change (Post-TRYP - Pre-TRYP) in behavioral outcome = treatment + pre-TRYP KYNA on test day + treatment x pre-TRYP KYNA, where the treatment x pre-TRYP KYNA on test day measures the change of slope for pre-treatment KYNA in predicting change in behavioral outcome. If this difference in slopes = 0, there is no mediator effect for pre-TRYP KYNA. Similarly, to assess mediation, we will fit a similar model to assess the difference between treatments (TRYP versus placebo) in slopes predicting change in the behavioral response from change in KYNA to whether change in KYNA mediates the treatment effect, noting that this is not the same as assessing causality (123).

Risks to Human Subjects

a. Human Subject Involvement, Characteristics and Design. The proposed project meets the definition of a “Clinical Trial.” This challenge study will enroll both healthy controls and people with schizophrenia. Following a period of baseline evaluation and assessment, participants (healthy controls and schizophrenia patients) will randomly participate in two visits. On one of the two visits, the participant will receive L-tryptophan (TRYP), and on the other visit the participant will receive placebo as an oral slurry. At each of the two visits, all participants will undergo morning baseline assessments followed by medication dosing, assessments and imaging procedures.

Potential Risks to Human Subjects:

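### The criterion named for KYNA mediation, a TRYP-placebo difference in slopes, tests whether the KYNA slope varies by treatment, and is zero when KYNA carries the whole effect with one common slope.

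*Combined protocol and SAP*

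**What the plan says.** All of this is in the combined protocol and SAP. Under Statistical Analysis, Secondary Aim 2, the moderation model is "change (Post-TRYP - Pre-TRYP) in behavioral outcome = treatment + pre-TRYP KYNA on test day + treatment x pre-TRYP KYNA". The plan then gives a reading rule: "If this difference in slopes = 0, there is no mediator effect for pre-TRYP KYNA". The sentence describes moderation but uses the word *mediator*.

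Mediation is handled by analogy: "to assess mediation, we will fit a similar model to assess the difference between treatments (TRYP versus placebo) in slopes". The sentence goes on to name "slopes predicting change in the behavioral response from change in KYNA to whether change in KYNA mediates the treatment effect", where some words seem to have dropped out. It ends by noting that this does not establish causality. Each diagnostic group is analysed separately, and the level is set by "We will conduct exploratory analyses at unadjusted two-sided alpha = 0.05".

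The plan says it follows a published approach, cited as item 118. In Literature Cited that item is a review of tryptophan loading; the paper on mediators and moderators in randomized trials is item 123.

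Primary Aim 1 is worded in terms of KYNA: "To determine if TRYP-induced elevated KYNA levels impair performance on neuropsychological measures". Its model has no KYNA term: "post-study drug score on i-th day = pre-study drug score on i-th day + treatment on i-th day + day + treatment x day".

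On sampling, Assessment Schedule states: "The laboratory assessments will be collected at pre-TRYP challenge baseline, and 30 min, 60 min and 90 min post ingestion". A last sample is drawn with the second cognitive battery, giving four post-dose samples. The plan does not say which one defines change in KYNA.

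**The concern.** Mediation needs two links: TRYP must raise KYNA, and KYNA must relate to behaviour once treatment is accounted for. The named criterion is neither link. It compares the second link between treatments and ignores the first.

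The simplest form of the study's hypothesis is one KYNA-behaviour relation, with TRYP moving people along it. That is the equal-slope case, in which the slope difference is zero by construction.

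What is at stake is interpretation. Primary Aim 1 attributes its effect to KYNA, and Secondary Aim 2 is the only place where the plan writes out a model linking KYNA to behaviour. If the criterion points at the wrong quantity, a true KYNA pathway could be reported as absent, or a slope difference without a KYNA rise could be reported as mediation.

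**Working it through.** **Inputs from the plan.** Planned enrolment is 50 per group with 10% attrition (Recruitment): 50 x (1 - 0.10) = 45 completers, which reproduces the plan's figure. Each completer has two visits. Alpha is 0.05, two-sided and unadjusted. The plan gives no KYNA variances, effect sizes or power for this analysis, so those inputs below are assumptions.

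**Algebra.** Let K be change in KYNA and D change in behaviour.

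- Placebo day: D = b_P x K + error
- TRYP day: D = c + b_T x K + error, where c is any effect not passing through KYNA
- KYNA rise: m = mean K on TRYP minus mean K on placebo
- Plan's criterion: b_T - b_P
- Indirect effect: b x m with a common slope b; b_T x m or b_P x m with separate slopes

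The criterion does not contain m. With b_T = b_P = b and c = 0, the total effect is b x m, all of it through KYNA, and the criterion is b - b = 0. With m = 0 the indirect effect is 0 whatever b_T - b_P is.

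**Simulation 1: complete mediation, equal slopes.** n = 45, 2,000 trials per row, random intercept, residual SD 1, within-person correlation 0.3, m scaled to 1 (so the total effect equals b). The joint test requires both the KYNA rise and the treatment-adjusted KYNA slope to be significant.

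| b | SD of K, TRYP day | SD of K, placebo day | Slope difference rejects | Joint test rejects |
|---|---|---|---|---|
| -0.5 | 0.5 | 0.1 | 5.4% | 42.8% |
| -0.5 | 0.5 | 0.5 | 5.4% | 65.2% |
| -0.5 | 1.0 | 0.1 | 4.2% | 92.0% |
| -0.5 | 1.0 | 0.5 | 5.2% | 95.7% |
| -0.8 | 0.5 | 0.1 | 5.1% | 77.8% |
| -0.8 | 0.5 | 0.5 | 4.4% | 96.3% |
| -0.8 | 1.0 | 0.1 | 4.3% | 99.8% |
| -0.8 | 1.0 | 0.5 | 4.9% | 100.0% |

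The Monte Carlo standard error at 5% is 0.5 points.

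**Simulation 2: other inputs.** Within-person correlation 0.4, m from 1 to 5, b from -0.3 to -0.5, 4,000 trials per scenario. Under complete mediation the slope difference rejects in 5.5% to 6.0% of trials, the small excess over 5% coming from a simple estimator. With no KYNA effect on behaviour at all it rejects in 5.2%. The criterion therefore cannot separate complete mediation with equal slopes from no KYNA effect.

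**When slopes differ.** With m = 2 and slopes of -0.8 on TRYP and 0 on placebo, the criterion rejects in 97.7%, so it does respond to this form of mediation. With m = 0, a placebo slope of 0 and a TRYP slope of -0.5 or -0.8, it rejects in 68.9% or 95.7% although the indirect effect is 0; the joint test rejects in 2.9% or 3.9%.

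**Smaller effects.** With the spreads of simulation 1 but an assumed total effect of 0.2 to 0.3 SD, the joint test detects roughly 10% to 63%.

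**Confounding.** With no KYNA effect on behaviour, a direct effect of -0.5, and an assumed correlation of -0.2 to -0.3 between KYNA change and the outcome residual, the joint test declares mediation in about 45% to 86% of trials. The rate depends on the KYNA spreads and is lower when placebo-day KYNA varies little, so read it as an order of magnitude.

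**Sample choice.** Six tests x 2 groups = 12 slope tests at one named sample; 12 x 0.05 = 0.6 false positives expected if nothing is there. If any of four samples may be used, 12 x 4 = 48 tests and 48 x 0.05 = 2.4.

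**The case against.** The strongest reply is that the plan is being held to a rule it does not state. The rule about a zero slope difference is written for pre-TRYP KYNA only. The mediation sentence is incomplete, a similar model would contain a KYNA main effect, and the cited methods paper, which is not available here, may add criteria. This stands in part. A reader might infer that the plan will report no mediation whenever the slopes are equal; the text does not go that far. But the slope difference is the only criterion written down. No test of the main effect is named and, with the interaction in the model and placebo as the reference, that term is the placebo-day slope and not a common one.

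A second reply is that missing 95% of cases is no measured harm. That is correct: it is 1 - 0.05 for any test of a quantity that is truly zero, and it applies only to equal slopes.

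Third, the contrast with the joint test is flattering at 0.5 to 0.8 SD. The sections on potential risks and on protections against risk expect only mild or slight cognitive effects, where the joint test is weak, and it is exposed to confounding. Both limits stand.

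Fourth, a zero KYNA rise runs against the study's premise and its pilot finding of a marked rise, though that pilot covered ten healthy controls and measured kynurenine, not KYNA. The overview also says that effects on peripheral pathway markers will be explored, so the KYNA rise is likely to be examined even though no model for it is written out.

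**Conclusion.** The concern holds as a minor point. The named criterion answers whether the KYNA slope varies by treatment. In the equal-slope case it rejects at about its nominal 5% however strong the mediation. That result follows from the algebra and does not depend on the assumed inputs; all the power and false-positive figures do.

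Two stronger readings are not supported. A reader might infer that the primary analysis is compromised; it is not, because the randomized TRYP-placebo comparison in Primary Aim 1 is valid without a KYNA term. A reader might also infer that the plan cannot detect mediation at all; it can when slopes differ. Whether the cited paper supplies further criteria cannot be settled from the documents.

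**What to change.** In each group, replace the mediation sentence with three estimates:

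- (a) the TRYP-placebo difference in change in KYNA, with 95% CI;
- (b) the slope of behavioural change on change in KYNA, from a model with treatment, day and participant;
- (c) the indirect effect, with a 95% CI from a bootstrap that resamples participants, using treatment-specific slopes if they differ.

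Keep treatment x change in KYNA only as a check that the slope is common, and state that a zero slope difference is not evidence against mediation. Name the post-dose sample that defines change in KYNA; the one drawn with the second battery matches the outcome in time. Change *mediator* to *moderator* in the pre-TRYP KYNA sentence, and correct the reference number for the method.

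The cost is a text change and a re-specified exploratory analysis, with no new data. Three downsides should be stated. The analysis stays exploratory. Power is low for mild effects: roughly 10% to 63% at an assumed 0.2 to 0.3 SD and about 42% or more at 0.5 SD, by the joint test, which only approximates the bootstrap interval. Unmeasured correlation between KYNA change and outcome can produce a false indirect effect, so the plan's caveat about causality must remain.

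This change does not supply a model for the HPA-axis and inflammatory indices named in Secondary Aim 2; that is a separate matter.
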